To assess the potential for telerehabilitation to enhance visual function by providing remotely-delivered LVR training to use magnification devices (i.e., hand-held or stand optical magnifiers, electronic magnifiers). Following basic LVR (i.e., one in-office training session) for new magnification device(s), we aim to determine if there is additional gain in visual functioning by randomizing subjects (2:1) to telerehabilitation or additional in-office LVR (active control). This will help provide estimates of effect size to plan a future larger-scale randomized controlled trial. We will compare visual function changes with the Activity Inventory questionnaire and validated reading tests in 60 LV patients with central vision loss due to any ocular disease recruited from 10 centers. Participants will be assessed before and after two consecutive periods: (1) no further training will be provided for one month after a single LVR training session (i.e., basic LVR), followed by (2) up to three LVR sessions over a three month period either via telerehabilitation (n=40) in the participants' homes with study loaner equipment (iPad/smartphone, stand, reading cards) via remote control assistance, or in-office LVR (active control; n=20). Multiple sessions will be conducted if the LVR provider deems the participant is not completely proficient with their magnification device. We will determine which patient characteristics and/or magnification devices are most likely to benefit from telerehabilitation, to be targeted in a future, larger-scale, phase III trial.

The primary goal of this proposal is to refine the methods and procedures for implementing these innovative technologies for LVR, in order to develop future protocols for randomized controlled trials. In the future, we envision that telerehabilitation could improve efficiency and patient outcomes by changing the method by which follow-up LVR services are provided. This is a high priority given the increasing prevalence of LV, paucity of LVR providers, and barriers related to transportation and geography.

Background and Significance: Provide a summary of the background for this study and explain how it will contribute to existing knowledge.

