will follow a standard protocol for the schedule of visits and number of sessions, but the intervention itself is considered standard of care. We considered using 'usual care' as a control but decided against it since there is no standard for the number of sessions and content delivered during the training, as much variability exists for the LVR practices of our providers; some do not tend to conduct multiple training sessions when new magnification devices are prescribed, while others will have one or more additional LVR session(s). Usual care comparator trials are also vulnerable to the Hawthorne effect in which practice may be influenced by the fact that providers are being studied. We are proposing the same standardized schedule of visits for both telerehabilitation and active controls in-office to keep the dosing of the interventions consistent in this parallel design trial. We anticipate that usual care will involve fewer LVR sessions and thus result in worse outcomes than a strict active control intervention, thus there is limited value to study usual care at this stage. Adding a third arm for usual care in the proposed trial would significantly increase the required sample size, which would be outside of the scope of this project. In the future, a much larger scale effectiveness trial can be designed to compare telerehabilitation to usual care practices.

Subjects and Magnification Devices:

Subject identification and recruitment will occur at all study sites. Adult participants will be recruited from the patients seen in the LVR service at four academic centers: (1) New England College of Optometry (NECO) in Boston, MA, (2) University of Nebraska Medical Center (UNMC) in Omaha, NE, (3) Southern California College of Optometry (SCCO) in Fullerton, CA and (4) University of California, Los Angeles (UCLA) and six private practices (Mid-Michigan Eye Care; Low Vision Services, PLC; See What You Miss Optometry; Frank Stein & Paul S. May Center for Low Vision Rehabilitation; Boston University Eye Associates, Inc.; Family Eyecare of Orange & Solinsky Eyecare LLC). Eligible patients will have newly received following types of magnification devices (multiple devices allowed): hand-held optical magnifiers, portable electronic video magnifiers, some stand magnifiers and CCTVs. Study screening, consent and enrollment procedures will only take place at UCLA and will only be conducted by the study team members at UCLA, which will include oral consent by phone.

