Our primary outcome measure, the Activity Inventory questionnaire, and the secondary outcome measure, the Sustained Silent Reading test by Ramulu et al., will be administered by phone by a UCLA research assistant at baseline (time of study entry), one month following receipt of the new magnification device, and four months after receipt of the magnification device (at time of study completion). The SF-36 general health questionnaire, Telephone Interview for Cognitive Status (TICS), Geriatric Depression Scale, and Hospital Anxiety Depression Scale questionnaires will be administered by phone by a UCLA research assistant at baseline (time of study entry), and four months after receipt of the magnification device (at time of study completion). The MNread test will be administered by the OD/OT provider at each in-office visit and/or during telerehabilitation sessions. Within 24 hours of each telerehabilitation session or in-office rehabilitation session, the UCLA research assistant will administer a satisfaction survey by phone. To characterize participants' baseline level of visual impairment, we will gather information from a medical record review from each our sites, in which we will record the results from validated visual acuity and contrast sensitivity tests at the initial in-office visit. These vision tests are used as part of standard of care.

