Per study visit/session to receive telerehabilitation or training in-office = approx. one hour

Per study telerehabilitation session to complete follow-up survey = approx. 15-30 minutes

Per study session to complete questionnaire outcome measures by phone = approx. 2-3 hours

Total anticipated time commitment per subject = approx. 8-15 hours over 4 months

Statistics and Data Analysis: Describe the proposed statistical procedures or descriptive analyses for the study. If applicable, indicate how the sample size was determined.

Data analyses: Data management will be an ongoing task for the PI.

Descriptive statistics will be used to summarize the study data and findings. We will determine the effect sizes for basic LVR (one session in-office as part of standard of care), additional in-office LVR (active control), and telerehabilitation for changes in the Activity Inventory and reading outcomes by comparing the scores at each follow-up to baseline (pre-LVR). For the Activity Inventory questionnaire, we anticipate that the reading domain may have the largest magnitude of change since magnification devices are most often used for reading tasks, which is the chief complaint of most LV

patients. For the MNread test, we will primarily focus our analyses on reading acuity and maximum reading speed. Separate analyses (sub-groups) for all outcomes will be used to compare outcomes for participants with hand-held or stand-based magnifiers (optical or electronic) versus spectacle-based high add power magnification (hands-free).

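### The plan does not settle whether baseline precedes device receipt and the first training session, and it measures the randomised interventions from that baseline instead of from month 1

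*Combined protocol and SAP*

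**What the plan says.** All references are to the combined protocol and SAP.

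- **Subjects and Magnification Devices**: "Eligible patients will have newly received following types of magnification devices". The same section says "Study screening, consent and enrollment procedures will only take place at UCLA", with oral consent by telephone.
- **Outcome measures**: the Activity Inventory (primary) and the Sustained Silent Reading test are given by telephone "at baseline (time of study entry), one month following receipt of the new magnification device, and four months after receipt of the magnification device". Baseline is therefore tied to study entry, and both follow-ups to device receipt.
- **Specific Aims**: in the first period, "no further training will be provided for one month after a single LVR training session". The stated aim is the gain that telerehabilitation or further in-office training adds once basic LVR has been given. Participants are to be assessed before and after each of the two periods.
- **Research Plan and Methods**: a run-in serves to assess basic LVR, and randomisation follows it. The section on hypothesised outcomes confirms that everyone has one in-office session before randomisation.
- **Statistics and Data Analysis**: "We will determine the effect sizes for basic LVR (one session in-office as part of standard of care), additional in-office LVR (active control), and telerehabilitation". All three are to be obtained "by comparing the scores at each follow-up to baseline (pre-LVR").

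**The concern.** Two separate problems arise.

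The first is timing. A patient who qualifies by already holding the device, and who is then enrolled by telephone from a central site, may be interviewed after first using the device and perhaps after the single training session. The analysis nevertheless treats that interview as preceding training. Basic LVR is given to everyone before randomisation, so its effect is an uncontrolled before-after difference. The baseline score is its only reference, and randomisation cannot repair a late one. With ten centres and central enrolment, the interval from receipt to interview may also differ between participants, so that baseline means different things for different people.

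The second is the choice of reference, and it remains even if every baseline is taken before training. A change from the pre-training score to month 4 contains the basic-session gain as well as whatever telerehabilitation or further in-office training added. The protocol's purpose is to supply effect sizes for a later, larger trial. That trial would then be planned on a gain partly achieved before the randomised interventions began.

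**Working it through.** **Step 1: the plan's own figures.** The plan gives no figure for the basic-LVR gain, for the interval from receipt to interview, or for how many interviews come late. There is thus no stated number to correct on this point. The only related figure is in the sample size paragraph: 18 subjects in each visual-acuity group, for a within-subject gain of 0.14 logits after telerehabilitation, SD of differences 0.17, power 0.80 and alpha 0.05. The normal approximation, two-sided, gives ((1.960 + 0.842) × 0.17 / 0.14)² = 11.6, so 12. The exact paired t calculation gives 14 two-sided and 11 one-sided. The stated 18 is not reproduced; at n = 18 the two-sided power is 0.908. That gap is on the conservative side and does not bear on the timing question.

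**Step 2: the sections side by side.**

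| Section | What it implies about baseline |
|---|---|
| Subjects and Magnification Devices | Device already received when the patient is eligible |
| Outcome measures | Interview at study entry; follow-ups counted from receipt |
| Specific Aims | First period begins after the single session |
| Research Plan and Methods | Basic LVR lies inside the run-in, so baseline comes before it |
| Statistics and Data Analysis | Baseline is pre-LVR |

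The first three allow a late baseline and the last two assume an early one. The month-1 clock also differs: Specific Aims counts from the session and Outcome measures from receipt. No available text says that these fall on the same day.

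**Step 3: what each difference estimates.** Let B be the mean gain from the state before device and training to month 1. Let E be the part of B already present in the average entry score. Let T and C be the mean changes from month 1 to month 4 under telerehabilitation and in-office training.

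- Month 1 minus entry = B − E. This understates B by E.
- Month 4 minus entry, telerehabilitation = B − E + T. It loses the same E.
- Month 4 minus month 1, telerehabilitation = T. E does not enter.
- Between-arm difference in month 4 minus entry = (B − E + T) − (B − E + C) = T − C. B and E cancel in expectation because entry and the basic session both precede randomisation.

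**Step 4: size of E.** If a proportion p of interviews are late and those participants already show on average a share q of the gain, then E = p × q × B and the basic-LVR estimate is (1 − pq) × B. The documents give neither p nor q. For scale only, put B = 0.14 logits. This is an assumption: the plan gives 0.14 as the target after telerehabilitation, not as a basic-LVR gain.

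| pq (assumed) | Observed basic-LVR gain |
|---|---|
| 0.10 | 0.14 × 0.90 = 0.126 |
| 0.20 | 0.14 × 0.80 = 0.112 |
| 0.30 | 0.14 × 0.70 = 0.098 |
| 0.50 | 0.14 × 0.50 = 0.070 |

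**Step 5: size of the reference problem.** Measured from entry, the telerehabilitation effect exceeds the additional gain T by (B − E + T) − T = B − E, or by the whole of B if baseline truly precedes training. If B and T were both 0.14 (again an assumption), the reported figure would be 0.14 + 0.14 = 0.28, twice the additional gain. The in-office figure is raised by the same amount. For these two effect sizes a late baseline works against the inflation and does not add to it.

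**The case against.** The strongest reply is that the intended order is clear. The run-in exists to assess basic LVR, participants are to be assessed before and after each period, and the analysis expressly labels baseline as pre-LVR. The eligibility sentence may only describe the population; it gives no sequence of receipt, consent and interview. Device receipt is also not the same as training, so an interview after receipt but before the session would still be pre-LVR. Finally, part of the text around the site procedures was not available for review, and a timing rule could stand there.

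Most of this stands. A reader might infer from the eligibility wording that every baseline follows both device and training, so that the basic-LVR estimate would largely vanish. The documents do not support that. They do not establish the order, they do not tie receipt to the session, and a total loss would need the whole gain to be present at once. The Activity Inventory asks about functioning and is repeated only after a month, so any gain that builds up over that month would remain in the estimate.

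The reply does not remove the conflict, because the evident intent has no rule behind it in the available text. Nor does it touch the choice of reference, which matters most when the intended order is kept.

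**Conclusion.** The point holds as an unreconciled statement of timing plus a reference that does not match the aim. If some baseline interviews follow receipt or the session, the basic-LVR effect is understated and month 4 minus baseline loses the same early part. The documents do not allow the amount to be computed, and the values in the working are only a range under stated assumptions. Independently of timing, the planned telerehabilitation and in-office effect sizes include the basic-LVR gain to the extent that baseline precedes it.

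A reader might also infer that the randomised comparison is biased. It is not: both arms share the same baseline process and basic LVR comes before randomisation. The change from month 1 to month 4 is likewise unaffected. The harm is confined to the run-in estimate and to within-arm changes referred to study entry. These matter because the trial exists to supply effect sizes. The conclusion is conditional on there being no timing rule in the text that was not available.

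**What to change.** 1. Reconcile Specific Aims, Research Plan and Methods, Subjects and Magnification Devices, Outcome measures, and Statistics and Data Analysis on the order of baseline interview, device receipt and first session. State whether month 1 is counted from receipt or from the session.
2. Record the dates of the baseline interview, device receipt and first session for every participant.
3. Use the month-1 score as the reference for the telerehabilitation and in-office effect sizes. The Activity Inventory and the Sustained Silent Reading test are already collected then. MNread is given at provider sessions and not at the month-1 call, so its reference must be named separately.
4. Report month 1 minus baseline as the basic-LVR effect only for participants whose interview preceded the session. Otherwise drop the pre-LVR label and describe the difference as change since study entry.

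The cost is protocol wording and three dates; the month-1 reference needs no new Activity Inventory or silent reading data. The downside is that the basic-LVR estimate rests on fewer participants, and possibly on a selected subset, so their number and characteristics should be reported beside it. Nothing here asks for the standard-of-care session to be delayed to fit an interview. The plan puts telephone outcome sessions at about 2 to 3 hours, so some interviews may not come first, and step 4 allows for that.

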We recently completed a pilot study of telerehabilitation for low vision, in which our first goal was to perform the initial steps to develop, administer, refine, and evaluate components required to deliver follow-up low vision telerehabilitation services. Three low vision providers (Drs. [name] and [name], and an OT) conducted telerehabilitation sessions from their office with ten visually-impaired older adults in their homes, who recently received a hand-held magnification device for reading and self-reported difficulty with returning for follow-up training at their provider's office. All except one participant had never used videoconferencing prior to our study, and three had never used the Internet. Participants and providers rated the use of loaner hardware devices (i.e., tablets, MiFi mobile hotspot) and HIPAA compliant, secure videoconference services during telerehabilitation sessions at which participants read MNread cards and received feedback on magnifier use. Drs. [name] and [name] reported little to no difficulty with evaluating participants' reading speed, reading accuracy and working distance with their magnifier. Both providers and participants rated both the audio and video quality as excellent to good with the iPad mini, which was noticeably better than the less expensive Android tablets we also evaluated. All participants agreed that they were satisfied and comfortable receiving telerehabilitation and evaluation via videoconferencing. Eight of 10 reported their magnifier use improved after telerehabilitation. All participants who had the session in their home reported they were very interested in receiving telerehabilitation services again if their visual needs change. Positive feedback from both participants and providers in this pilot study supports the feasibility, acceptability and potential value of LV telerehabilitation.

Surveys of LV patients' Interest in Telerehabilitation at our proposed sites:

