All participants from our 10 clinical centers will use the study loaner devices to access the telerehabilitation session, rather than their own Internet-enabled device. Telerehabilitation sessions will be facilitated by a remotely located member of our study team at UCLA who will use remote access control provided by RescueAssist by LogMeIn to initiate/end the zoom videoconference session on the study loaner smartphone that they will receive in order to conduct the telerehabilitation session. This option would not require the participants to do anything on the smartphone to access the videoconference session (it can be completely set-up via our remote access control); all the participant would need to do at the scheduled time of the telerehab session is put the smartphone in the stand that will be provided to them when they join the study and orient the camera on the smartphone so the study team involved with the telerehabilitation session can see the participant using the magnifier. At the time of the scheduled telerehabilitation session, the UCLA study team member who will use Rescue Access remote control access will call the participant by phone to confirm their willingness to start the session prior to initiating the videoconferencing. We will print copies of the near reading card and MNread test cards, place them in a sealed envelope, provide it to the participant when they receive the study loaner smartphone, and the participant would open/use the reading card print-outs during the telerehabilitation session. We will continue to use secure and HIPAA compliant videoconference services from zoom.us (UCLA Health Zoom), which is accessible across Windows, Mac, iOS, Android, Blackberry, and Linux platforms on desktop, tablet, and mobile devices to enable our study team to use their device of preference. A private meeting code will be used to access the videoconference portal for the sessions. For security, the sessions will not be video-recorded, but a student research assistant will take notes. All sessions will take place in the subjects' home. Each session will last about an hour. LVR providers from all of our 10 clinical centers will administer the MNread test to their respective patients and will evaluate the participant's reading

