technique (i.e., working distance, lighting) and reading fluency (i.e., speed, accuracy, print size) with their magnifier device. In addition, they will ask the participant to read or view their own materials of interest, while providing LVR training. If relevant, the providers will ask participants to demonstrate how to change the battery in the magnification device, or to walk around their home with the smartphone to show the illumination levels in places where they use their magnifier. We will continually assess the telerehabilitation survey responses we will collect from both the LVR providers from our clinical centers and participants, in order to resolve any reoccurring problems related to Internet connectivity, videoconference portal, hardware devices, or audio/visual quality.

Hypothesized Outcomes, Sample Size Calculation and Data Analyses

Our outcomes that are questionnaires or reading tests will be assessed by phone by a different UCLA research assistant at each evaluation. It is not possible to mask the participants or LVR providers. The outcomes assessors will be identically trained by the PI. We successfully administered reading tests by phone in a previous study by providing the materials in a sealed envelope that the subject opens only at the test exam time. Our two interventions (telerehabilitation versus additional in-office LVR) may have similar effects since the same LVR principles will be applied at the same planned schedule of sessions; however, it is possible that telerehabilitation may be more beneficial if compliance with scheduled sessions is better than in-office LVR and/or if home-based training is advantageous in the patient's own environment with relevant tasks of interest; on the other hand, there may be aspects of LVR training that work better in-person and in-office. In-office LVR or at-home LVR with a therapist in-person are currently considered standard of care. All participants will receive standard of care since they will all receive one in-office LVR training session prior to randomization.

Outcome measures

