The PI will be responsible for training the research assistants in basic interview skills and instructions for administering the survey instruments, as well as internal quality assurance measures. To help assure the quality and consistency of responses from participants for our primary and secondary outcomes, the PI will instruct the research assistants involved in data collection to adopt a neutral demeanor and interviewing style when administering the questionnaire (i.e., avoid directing, guessing responses; suspend judgment, but not standoff-ish). The PI will periodically observe about 10% of the survey administrations throughout the study to confirm they are being conducted consistently and according to instructions. The research assistants will be trained to respond to possible depression or suicidality by connecting the at-risk participants to someone by phone by either calling 911 or someone at the National Suicide Prevention Lifeline. If a subject indicates suicidal ideation and indicates that they have means and intent to accomplish this, the study team will keep the subject on the telephone while asking another study team member in the participant's local area to telephone 911 for immediate intervention. If the study team encounters a subject who expresses suicidal ideation or suicidal intent, they will keep the subject on the phone call until they are able to transfer the subject to speak to a specialist at the National Suicide Prevention Lifeline. In the case of severe depression or anxiety, we will refer them to see their internist or general physician so they can find appropriate care locally. The cut-off scores that will trigger referral are ≤ 38 for the SF-36 mental component summary, ≥ 12 for the Geriatric Depression Scale, and ≥ 11 for the Hospital Anxiety Depression Scale (HADS-D). These three questionnaires will be scored while the subject is still on the telephone and study personnel will let the subject know that they will be making the referral for

follow-up evaluation with their primary care provider.

Procedures at each study site

- Marshall B Ketchum University, Southern California College of Optometry: subject identification, recruitment, conduct of vision rehabilitation training sessions in-office or via telerehabilitation, and data collection procedures from in-office visits

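### After randomization MNread is given by the treating provider at home by video in one arm and in the office in the other; the phone-administered Sustained Silent Reading test should carry the between-arm reading comparison

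*Combined protocol and SAP*

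**What the plan says.** All references are to the combined protocol and SAP.

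- **Who gives MNread, and where.** Outcome measures: "The MNread test will be administered by the OD/OT provider at each in-office visit and/or during telerehabilitation sessions". Telerehabilitation Methods agrees on the tester: "LVR providers from all of our 10 clinical centers will administer the MNread test to their respective patients".
- **Conditions in the telerehabilitation arm.** Telerehabilitation Methods: "We will print copies of the near reading card and MNread test cards, place them in a sealed envelope", which the participant opens and reads from during the video session. The same section adds: "All sessions will take place in the subjects' home". Control sessions are in the office (Specific Aims).
- **General rule on assessment.** Under Hypothesized Outcomes, Sample Size Calculation and Data Analyses, the plan sets this rule: "Our outcomes that are questionnaires or reading tests will be assessed by phone by a different UCLA research assistant at each evaluation". The same paragraph says that neither participants nor providers can be masked.
- **Number and timing of sessions.** Specific Aims allows up to three sessions over three months, with repeats when the provider judges that proficiency is incomplete. The available text gives no fixed month-4 MNread.
- **The other reading test.** Outcome measures ranks "the secondary outcome measure, the Sustained Silent Reading test" alongside the primary Activity Inventory. Both are given by phone by a research assistant at study entry, month 1 and month 4, in both arms.
- **Planned analyses.** Specific Aims compares changes on reading tests, in the plural and unnamed. Statistics and Data Analysis plans effect sizes for reading outcomes as change from a pre-rehabilitation baseline, singles out two MNread scores (maximum reading speed and reading acuity), and regresses a reading speed that is tied to no instrument.

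**The concern.** If the arms are tested under different conditions, a difference in MNread change cannot be attributed to the mode of training. It could reflect home lighting, printed copies, the video link or the office. The protocol itself gives reason to think that setting matters: Background and Significance says that skills learned in the office may not carry over to the home, partly because of lighting and ergonomics.

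The tester adds a second problem. In both arms it is the provider who delivered the training and knows the allocation. The number and timing of MNread measurements also depend on that provider's view of proficiency.

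What is at stake is planning. Specific Aims says the trial should supply effect sizes for a larger trial, and Background and Significance says that trial may be an equivalence trial of these two modes. A setting shift in MNread could imitate a difference between modes or hide one.

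**Working it through.** **Step 1: set the test conditions side by side.**

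| | MNread, telerehabilitation | MNread, control | Sustained Silent Reading, both arms |
|---|---|---|---|
| Setting and mode | Home, by video | Office, in person | Phone |
| Materials | Printed copies from an envelope | Not described | Same plan in both arms |
| Tester | Treating provider, unmasked | Treating provider, unmasked | Research assistant |
| Times | Up to three sessions | Up to three sessions | Entry, month 1, month 4 |

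For MNread, setting and mode follow the arm. For the Sustained Silent Reading test they do not.

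**Step 2: is the baseline in the office?** Effect sizes are taken from a pre-rehabilitation baseline, and telerehabilitation begins only after the in-office session and a one-month run-in. A pre-rehabilitation MNread, if there is one, could then come only from an office visit. But the records taken from the initial visit are listed as visual acuity and contrast sensitivity, not MNread. An office baseline is implied and not fixed.

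**Step 3: how sensitive would the estimates be?** The documents give no SD, effect or setting shift for MNread, and their only sample-size figure concerns the Activity Inventory, so there is no plan figure to reproduce here. Set the change-score SD to 1 in both arms and use the planned 40 and 20.

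- Between arms: SE = √(1/40 + 1/20) = √0.075 = 0.274, with 58 df. The 95% half-width is 2.002 × 0.274 = 0.548.
- Within telerehabilitation: SE = 1/√40 = 0.158, with 39 df. The 95% half-width is 2.023 × 0.158 = 0.320.

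Let the setting shift be s SD. Coverage of a nominal 95% interval is P(|T| < critical t), with T noncentral t and noncentrality s/SE. For s = 0.3 the noncentrality is 0.3/0.274 = 1.10 between arms and 0.3/0.158 = 1.90 within.

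| Assumed shift s | Coverage between arms | Coverage within telerehabilitation (office baseline only) |
|---|---|---|
| 0.1 | 0.935 | 0.905 |
| 0.2 | 0.889 | 0.765 |
| 0.3 | 0.810 | 0.543 |
| 0.5 | 0.565 | 0.131 |

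Coverage reaches 0.90 at s = 0.182 between arms and s = 0.106 within. A simulation of 40,000 runs agreed at 0.2, 0.3 and 0.5 (0.890, 0.809, 0.565 between; 0.763, 0.539, 0.132 within).

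**Step 4: what if some telerehabilitation patients are still tested in the office?** If a fraction f are, the mean shift is (1 − f)s, ignoring the extra variance from mixing. At s = 0.3 and f = 0.5 it is 0.15, with coverage 0.916 between arms and 0.848 within. At f = 1 the setting component vanishes and both return to 0.950.

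Every s and f here is an assumption. The tables show sensitivity; they are not evidence that a shift exists.

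**The case against.** The strongest replies are these.

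- **The reading tests are already ranked.** Outcome measures makes the Sustained Silent Reading test secondary and gives MNread no rank. This stands, and a reader should not infer that no reading outcome was designated. What is missing is the link from that ranking to the analysis section, which singles out MNread scores and leaves its reading speed unnamed.
- **No confounded test is specified.** A reader might infer that a between-arm MNread test is planned. The only arm test spelled out is for the Activity Inventory. MNread enters through the plural reading tests in Specific Aims and the planned effect sizes, so the risk lies in how those estimates are used.
- **The within-arm shift may not exist.** If the first study MNread is at the first home session, change across home sessions has one setting. This stands, so the within-arm figures are conditional.
- **A common-setting MNread may exist.** The and/or in the MNread sentence allows one. The available text also breaks off in Procedures at each study site, after an entry covering "data collection procedures from in-office visits"; removed text cannot be counted as missing from the plan. This too stands.
- **The pilot used MNread by video.** Its sessions were ones "at which participants read MNread cards and received feedback on magnifier use". That supports feasibility in ten participants but gives no comparison with the office.
- **The general rule covers reading tests.** It conflicts with provider-administered MNread, but the MNread sentence is specific enough to settle who tests. A clarifying clause is enough.

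**Conclusion.** The point holds as a minor one. On the available text, an MNread arm contrast mixes training with test setting and relies on an unmasked treating provider, at session-dependent times with no fixed month-4 measurement. The telerehabilitation arm's own MNread change shares the setting problem only if its baseline was taken in the office.

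Size and direction are unknown. The coverage figures rest on assumed shifts, equal SDs and 40 versus 20 participants.

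Three stronger readings are not supported:

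- **That the trial's main result is compromised.** The Activity Inventory is primary and, like the Sustained Silent Reading test, has the same mode and times in both arms. This is a phase 1/2 trial sized on the Activity Inventory.
- **That naming the Sustained Silent Reading test cures MNread.** It moves the between-arm inference to a measure without the setting confound; MNread stays as it is.
- **That office testing of everyone would remove all difficulty.** It would remove the setting component, but the unmasked provider and the lack of a fixed month-4 MNread would remain.

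**What to change.** 1. In Statistics and Data Analysis, specify the phone-administered Sustained Silent Reading test as the reading outcome for between-arm comparisons and as the reading measure in the regressions. State the score it yields, which the documents do not give.
2. Report the two MNread scores as supportive and descriptive. State the difference in setting and that the tester is the unmasked treating provider. Do not carry them into the future trial as clean effect sizes between modes. Say where the baseline MNread is taken. If a common-setting MNread exists, say so in Outcome measures and use it, still noting the tester and the timing.
3. Add one clause reconciling the general phone-assessment rule with provider-administered MNread.

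The cost is about two sentences and a clause, with no new visits, tests or data. What is given up is clean inference on the MNread measures. Reading acuity has no replacement.
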